F. 9-month telephone call – A telephone call will be made at 9 months (+/- 2 weeks) to review compliance and assess for any adverse events that may not have been previously reported (See Adverse Event reporting section). After successful completion of this call, an additional 3 month +/- 2-week supply of GH will be shipped to the subject.

12-month visit - The subject will return to CCHMC 12 months (+/- 2 weeks) after initiation of GH therapy for a repeat visit. The subject will undergo a routine physical examination including a focused joint exam (inspection of the hip joints, checking for scoliosis) and pubertal staging performed by a pediatric endocrinologist. Vital signs will be obtained. Weight will be measured on a digital scale. Height will be measured in triplicate on a standing stadiometer which is calibrated daily. The average of the three measurements will be used. A funduscopic exam will be performed. Labs will be performed as detailed in **Table 1**.

Table 1: Lab and Assessment Schedule for treatment year 1

Lab/Assessment	Screening Visit	3-month TC/remote lab visit	6-month visit	9-month TC	12-month visit
Physical Exam	X		X		X
Vital Signs	X		X		X
Weight	X		X		X
Height	X		X		X
CBC	X				
Renal Panel	X				
Hepatic Function Panel	X				
TSH	X		X		X
Free T4	X		X		X

IGF-1	X	X	X		X
IGFBP-3	X		X		X
Photographs	X				
Bone Age X-ray	X				X
Musculoskeletal Exam	X				
DXA scan (whole body and lumbar spine)	X				X
IKDC Knee Score	X				
QOL Survey	X				
Physical Activity Assessment (Marx)	X				
Oswestry back survey	X				
Compliance Review		X	X	X	X
Adverse Event Review		X	X	X	X
MRI	X				
Knee X-rays	X				

After each in-person study visit, we will send a letter summarizing the exam findings and lab results to the participant's local primary care physician and/or pediatric endocrinologist.

Stopping Rules and Dose Reduction Criteria

The treatment portion of the trial will be discontinued for an individual subject if he or she develops a serious adverse drug reaction (as defined below). The treatment trial may otherwise be discontinued if the subject withdraws consent or if the PI determines that the subject is no longer eligible to continue treatment.

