Reasons for Completion of the Clinical Trial Participation

When it becomes clear that a participant is no longer benefitting from ongoing GH therapy, treatment will stop.

To discontinue further GH therapy during the extension trial, either of the following must occur:

1. The participant reaches skeletal maturity according to their most recent bone age x-ray.
2. The participant has a height velocity of <2.5 cm/yr.
3. The participant and/or his/her family feels continued therapy does not lead to satisfactory treatment response.
4. The participant has completed their last study visit (3 year) and there is no more funding to continue the trial.

The treatment portion of the trial will be discontinued for an individual subject if he or she develops a serious adverse drug reaction (as defined below). The treatment trial may otherwise be discontinued if the subject withdraws consent or if the PI determines that the subject is no longer eligible to continue treatment. Participants that discontinue the treatment portion of the trial will be encouraged to follow up with their local pediatric endocrinologist for follow-up care and management.

If a subject's participation (and treatment) ends due to 1) completion of the trial and/or 2) lack of continued funding, study staff will work with the family to establish clinical care and GH treatment through a local pediatric endocrinologist. Up to 3 months' worth of medication and supplies can be dispensed to the family at the last study visit to ensure continuity of ongoing care during this transition period.

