8. RISKS/BENEFITS

The primary benefit of this study is the expected increase in growth rate in individuals treated with GH therapy. Subjects will be provided with a copy of their growth data and growth chart at each visit. Additionally, after each visit, a letter will be sent to the subject's primary care physician detailing the exam findings and laboratory results from that visit. Additionally, this study will provide us additional insights into the clinical presentation of ACAN deficiency which may benefit subjects and their family members in the future.

The major risks from this trial are related to the treatment with GH itself. Known side effects of this FDA-approved medication include mild edema, intracranial hypertension, slipped capital femoral epiphysis (SCFE), progression of scoliosis, and injection site reactions.

- Edema: Edema is usually mild and self resolves. Subjects will be asked about foot swelling. If edema persists and is painful, the dose of GH will be decreased 10-20%. If the edema continues to persist 2 weeks after decreasing the dose and is impacting the subject's daily activities, GH will then be discontinued.
- Intracranial hypertension: A funduscopic exam will be performed at baseline and at each follow up visit. In the case of persistent headache +/- blurred vision or vomiting, the patient will be referred to a local ophthalmologist for dilated eye exam to rule out papilledema. If papilledema is present, the subject will then be referred to a local emergency department for further evaluation including lumbar puncture. If papilledema is present, GH will be immediately discontinued. After the complete resolution of all headache symptoms and the complete resolution of papilledema, GH can be restarted at a reduced dose of 30 micrograms/kg/day. If the patient tolerates this dose for 2 months without recurrence of symptoms, then the dose can be increased back to 50 micrograms/kg/day. If at any point papilledema recurs, GH will be permanently discontinued.
- SCFE: A hip exam will be performed at baseline and at each follow up visit. If the patient develops hip or knee pain at any time during the study a hip X-ray will be obtained to rule out SCFE. If SCFE is present, GH will be immediately discontinued.
- Progression of scoliosis: A back exam will be performed at baseline and at each follow up visit. If the patient develops clinically significant scoliosis during the study, the patient will be referred to an orthopedic physician for

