A clinical laboratory AE is any clinical laboratory abnormality regarded as clinically significant i.e., an abnormality that suggests a disease and/or organ toxicity and is of a severity, which requires active management, (i.e., change of dose, discontinuation of trial product, more frequent follow-up, or diagnostic investigation).

Serious Adverse Event (SAE):

A serious AE is an experience that at any dose results in any of the following:

- Death

- A life-threatening* experience
- In-patient hospitalisation or prolongation of existing hospitalization
- A persistent or significant disability/incapacity
- A congenital anomaly/birth defect
- Important medical events that may not result in death, be life-threatening*, or require hospitalisation may be considered an SAE when, based upon appropriate medical judgement, they may jeopardise the subject and may require medical or surgical intervention to prevent one of the outcomes listed in this definition.
- Suspicion of transmission of infectious agents

*The term life-threatening in the definition of SAE refers to an event in which the subject was at risk of death at the time of the event. It does not refer to an event which hypothetically might have caused death if it was more severe.

Serious Adverse Drug Reaction (SADR):

An adverse drug reaction (ADR) is an adverse event (AE) for which a causal relationship to the trial product is at least possible i.e., causal relationship is conceivable and cannot be dismissed. Serious adverse reaction (SAR): Adverse event which fulfils both the criteria for a Serious Adverse Event and the criteria for an Adverse Reaction.

Suspected Unexpected Serious Adverse Reaction (SUSAR):

An SAE which is unexpected and regarded as possibly or probably related to the trial/study product by the investigator.

Medical Events of Special Interest (MESI): A MESI is (1) a medication error (e.g., wrong drug administration or wrong route of administration) or (2) a suspected transmission of an infectious agent via the product.

Non-Serious Adverse Event:

A non-serious AE is any AE which does not fulfil the definition of an SAE.

Severity Assessment Definitions:

- Mild: Transient symptoms, no interference with the subject's daily activities
- Moderate: Marked symptoms, moderate interference with the subject's daily activities
- Severe: Considerable interference with the subject's daily activities, unacceptable

Relationship to study medication Assessment Definitions:

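### If a first papilledema episode qualifies as a serious adverse drug reaction, the stopping rule discontinues treatment without exception, Section 8 permits restart and return to full dose, and nothing says which governs

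*Combined protocol and SAP*

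**What the plan says.** **Stopping rule.** Section 5, under Stopping Rules and Dose Reduction Criteria, states: "The treatment portion of the trial will be discontinued for an individual subject if he or she develops a serious adverse drug reaction". Section 6, under Reasons for Completion of the Clinical Trial Participation, repeats the sentence for the extension and adds: "Participants that discontinue the treatment portion of the trial will be encouraged to follow up with their local pediatric endocrinologist". Neither place gives an exception, a way back to treatment, or a reference to Section 8.

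**Intracranial-hypertension rule.** Section 8 lists intracranial hypertension among the known side effects of GH and sends a child with papilledema to an emergency department for work-up that includes lumbar puncture. It then sets a sequence:
- "If papilledema is present, GH will be immediately discontinued".
- After headache and papilledema have fully resolved, "GH can be restarted at a reduced dose of 30 micrograms/kg/day".
- If that dose is tolerated for two months, "then the dose can be increased back to 50 micrograms/kg/day".
- "If at any point papilledema recurs, GH will be permanently discontinued".

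Section 8 does not mention the stopping rule.

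**Definition.** Under its entry for a serious adverse drug reaction (SADR), Section 9 requires that a "causal relationship to the trial product is at least possible" and describes an "Adverse event which fulfils both the criteria for a Serious Adverse Event and the criteria for an Adverse Reaction".

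**Extension dosing.** Section 6, under Study protocol, says the 50 micrograms/kg/day dose may be changed only under the year-1 safety guidelines, which it equates with an IGF-I above +2.5 SD.

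**The concern.** Two operative safety instructions cover one foreseeable event and lead to different treatment. One ends the child's treatment in the trial. The other allows re-exposure to GH, up to the full dose. Which one applies turns on a seriousness and causality classification that Section 8 never mentions.

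Two things are at stake. The first is conduct. Section 9 provides no data safety monitoring board and assigns event review to the sponsor-investigator or, in that person's absence, a co-investigator. Different people could therefore reasonably apply different rules. The second is the data. Section 9 asks children who stop GH to continue assessments to the 3-year visit, so the child would still contribute a 36-month height. The choice of rule would decide whether that height was reached on or off treatment.

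**Working it through.** This is a comparison of texts. The plan states no figure on the point, so there is none to reproduce.

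**Step 1. Can a first papilledema episode be a SADR?** Section 9 sets two conditions.
- Causality must be at least possible. Section 8 names intracranial hypertension as a known GH effect, so a possible link would be hard to dismiss. It is still assessed per event, and unlikely is one of the available categories.
- The event must be serious. Admission to hospital would meet this. So could the important-medical-event clause, which is left to medical judgement. Section 8 requires emergency referral and lumbar puncture but does not say that the child is admitted.

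The overlap is plausible but not automatic.

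**Step 2. Apply the rules to each case.**

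| Case | Sections 5 and 6 stopping rule | Section 8 | Result |
|---|---|---|---|
| First episode, judged serious and at least possibly related | Treatment portion discontinued | Stop, then restart permitted at 30 and return permitted to 50 micrograms/kg/day | Conflict |
| First episode, judged not serious or unlikely to be related | Not triggered by this event | As above | No conflict with the SADR stop |
| Recurrent papilledema | Discontinued if a SADR | Permanently discontinued | Same outcome |

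The conflict is confined to the first row.

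**Step 3. Is the stop in Sections 5 and 6 final?** The word permanently is absent. What is discontinued, however, is the treatment portion of the trial and not a dose, and Section 6 then points such participants to local care. Both features read as an end to study treatment. This is an inference from the wording.

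**Step 4. Does Section 6 leave room for the restart in the extension?** Its reference to year-1 safety guidelines might be taken to include Section 8, but the gloss that follows names only IGF-I above +2.5 SD. The IGF-I rule in Section 5 works in reductions of 10% to 20%. A restart at 30 in place of 50 is a reduction of 1 − 30/50 = 0.40, or 40%, so it is not an instance of that rule. Read literally, Section 6 does not accommodate the restart, whether or not the episode is a SADR.

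**Step 5. What share of the data is affected?** Section 5 states that all 10 subjects are past one year of treatment, so a future event can no longer affect the 12-month outcome. At 36 months one child is 1/10 = 10% of the cohort. The share is larger if fewer than 10 entered the extension, a number the documents do not give.

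**The case against.** The strongest reply is that the wording of Section 8 is permissive. An investigator who stops GH after a first SADR and never restarts it breaches neither rule. That is correct, and it means the two rules are not a pair of opposing commands. But the permission is conditioned only on resolution of signs and symptoms, with no carve-out for serious reactions, and permanent discontinuation is stated only for recurrence. An investigator who relies on that text restarts a child whose treatment Sections 5 and 6 have discontinued.

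A second reply is that discontinued may mean a temporary stop, since Section 8 uses the same word for a reversible one. A reader might conversely infer that the stopping rule ends GH for good in express terms. The documents do not say that: permanence is the more natural reading of Sections 5 and 6, but it is inferred. If a hold was intended, the text should say so.

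Third, a case would have an identified decision-maker. Section 9 sets 24-hour review of serious events, and Sections 5 and 6 let the principal investigator judge continued eligibility. This stands and limits the practical risk, but the decision-maker would still have two texts to choose between.

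Finally, a reader might take the different criteria in Section 8 for restart, dose step and permanent stop as a further contradiction, or object to the timing of eye examinations. Those criteria govern three separate decisions and no sections conflict over them. They are clinical matters outside this point.

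**Conclusion.** The inconsistency is real but conditional: the stopping rules are contradictory as written for a first episode of intracranial hypertension with papilledema that meets the SADR definition. For that child an investigator cannot give effect to both the stopping rule and the restart permission, and in the extension the dose-adjustment limit in Section 6 does not fit the restart either.

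The conclusion assumes that discontinuing the treatment portion is not a temporary hold, and that the SADR entry in Section 9, which words the combined term as a serious adverse reaction, defines the term used in the stopping rule.

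Stronger readings are not supported. It cannot be said that every papilledema episode meets two opposite rules, because seriousness and causality are judged case by case. Nor can it be said that sites would diverge, because Section 5 describes a single-center study. The 12-month primary outcome is not exposed, because all 10 subjects have passed that point.

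The effect on the data is limited to one child of at most 10 per event, in the 36-month height SDS. Section 11 plans descriptive outcomes with no formal comparison, so no test result depends on it. The main reason to act is that this is a safety instruction for children.

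**What to change.** Reconcile Section 5 (stopping rules), Section 6 (extension dosing and reasons for completion), Section 8 (intracranial hypertension) and Section 9 (SADR definition) in one short amendment that:

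1. states which rule governs intracranial hypertension meeting the SADR definition;
2. says whether discontinuing the treatment portion is final or can be reversed;
3. brings the extension dose-adjustment sentence in Section 6 into line with whatever is decided;
4. cross-refers the sections to one another.

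Which rule applies is for the sponsor-investigator and the IRB, and this review takes no view on it. The change needs no added patients, visits or analyses. Its cost is the IRB and IND amendment paperwork.

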5. RESEARCH DESIGN AND METHODS

Study Hypotheses:

1. Treatment with GH therapy will increase growth velocity in children with ACAN deficiency.
2. Early joint pathology will be evident on MRI examination of affected subject's knees and will provide insights into the underlying joint pathophysiology present in ACAN deficiency.

Endpoints:

- A. Primary Outcome – Change in height SDS from baseline to 12 months.
- B. Secondary Outcomes
 - a. Height velocity in cm/year calculated over 12 months of trial.
 - b. Change in height velocity. Baseline height velocity will be based on review of the medical records using the documented height closest to 12 months prior to the screening visit.
 - c. Change in bone age divided by change in chronological age.
 - d. Change in whole body bone mineral density adjusted for height.
 - e. Frequency of adverse events as defined below
 - f. Frequency of joint complaints using measures described below.
 - g. Frequency of cartilage disease based on MRI evaluation of the knee as described below.

Study type

This is an open-label single arm prospective study examining the effects of a single dosing regimen of daily GH on growth response over a 12 month –followed by a four-year extension period in children with ACAN deficiency. The projected dose of GH that will be used is 50 micrograms/kg/day. This dose was initially chosen as it is within the approved range for Norditropin® for non-GH deficient states, including Turner Syndrome and Noonan Syndrome. Additionally, a parallel phenotyping study was done in affected first degree relatives of the subject.

We have elected not to have a control arm for two reasons. First, our preliminary retrospective data suggests that GH does increase HV in patients with ACAN deficiency. Additionally, the retrospective data show that patient's height SDS score will decline over time without intervention. Thus, patients and their families are highly motivated to pursue GH therapy and are unlikely to consent to be part of a study which includes a control arm. Near one-hundred percent compliance (limited missed daily GH injections) and persistence with the protocol has been observed in our cohort so far for patients at least one year on therapy and as long as 30 months. Second, this is a rare disorder, and we did not think it is feasible to recruit sufficient numbers of patients in a reasonable time frame to conduct an adequately powered randomized controlled trial.

.

Study population

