The dose of GH will be adjusted based on weight at study visits. It will not be increased or decreased based on efficacy (or lack thereof) with the following exceptions: at the 3, 6, 18 month and any added remote lab draw, if the IGF-I exceeds +2.5 SD, the GH dose will be reduced. Reductions will be 10%- 20% at the discretion of the PI, depending on the extent of IGF-I elevation. In the unlikely event that the IGF-I remains above the +2.5 SD mark at the next check, the dose will be further decreased by either 10%-20% and an additional IGF-I level will be checked at the PI's discretion.

Joint Phenotyping Procedures for Subjects and Relatives

The goals of the joint phenotyping protocol are twofold. First, we would like to comprehensively assess the prevalence of joint complaints in this patient population with specific focus on the knee joint. Second, we would like to examine the early radiological manifestations of joint disease in these patients by using a cartilage-focused MRI without contrast protocol at the knee. These imaging studies will provide insights into the pathological effects of mutations in ACAN on joint cartilage. Once arthritis is

advanced, the MRI findings will no longer be specific or instructive, so we will only perform MRI assessments in individuals under age 20 years.

We are focusing our investigations on the knee joint for two reasons. First, retrospective data show that the knee joint is the most commonly involved joint in ACAN deficiency associated arthritis⁵. Second, the other joint(s) with significant pathology in ACAN deficiency are the intervertebral joints in the back. These joints have many normal variants on MRI imaging, and we think it will be difficult to determine which MRI findings represent true pathology versus normal variation. We will perform a thorough musculoskeletal evaluation through physical examination (for those who are able to do the assessment based on age and/or ability) and questionnaires which will include all joints (see below). We believe that MRI examination of the knee is most likely to provide insights into the pathophysiology of ACAN associated joint disease.

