All first-degree relatives will be screened for the ACAN mutation identified in the primary subject in the family. More distant relatives will be offered inclusion in the study at the discretion of the subjects' parents and [name]. This genetic testing will be performed as part of a separate genetics protocol. Any family member identified to carry the same mutation as the primary subject will be eligible for inclusion in the phenotyping protocol. If a family member meets inclusion criteria for the GH treatment trial, they also will be offered the option of enrolling in the treatment trial. Eligible family members will come to CCHMC for a single research visit where they will undergo a detailed phenotypic evaluation as detailed below. This evaluation will be scheduled to coincide with one of the primary subject's research visits. We estimate that each subject will have one affected parent and one affected individual giving us a potential total of 30 affected individuals undergoing joint phenotyping (~20 of whom will be under 20 years old).

The detailed phenotyping evaluation includes the following assessments:

1. Height – Measured in triplicate on a standing stadiometer which is calibrated daily. The average of the three measurements will be used.
2. Weight – Measured on an electronic scale.
3. Detailed musculoskeletal evaluation performed by physical therapist including the IDKC knee score (a validated knee instrument), Oswestry back survey, a 3-dimensional biomechanical and gait assessment.
4. Questionnaire regarding medical history with specific attention to growth and joint issues as well as a validated quality of life survey (Peds QL) and physical activity assessment questionnaire (Marx).
5. Photographs
6. Radiographs
 - a. Standard 4 view X-ray series of the knees in all affected individuals.
 - b. Subjects under 20 years of age will have a bone age performed.
7. 3T MRI of the knees will be performed on all subjects who are able to do the assessment without sedation (per Radiology generally age 6 and older) under

age 20 years to look for early evidence of joint disease. For all subjects, a standard MRI checklist will be used to assess eligibility prior to scheduling any study visits. Subjects can enroll and participate in the study even if they are not able to undergo the MRI procedure.

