Specifically, we will use a combination of MRI sequences which are specifically designed to look at cartilage. We will begin with T2 relaxation time mapping (T2 mapping), a quantitative MR technique, highly sensitive to changes in collagen content and anisotropic orientation of collagen fibers within the cartilage ^{7,8}. T2 mapping allowed early detection of cartilage changes in JIA which was not predictable either on conventional MR or clinical exams ^{9,10}. Additionally, T_{1ρ} imaging is a promising new technique, highly sensitive to the interaction of water molecules with glycosaminoglycan (GAG). By measuring collagen fiber anisotropic changes (reflected by increased T2 values) in combination with GAG depletion (reflected by increased T_{1ρ}), we can obtain a complete set of information of hyaline cartilage ¹¹⁻¹⁵. Finally, we will use diffusion tensor imaging (DTI), a noninvasive technique enables measurement of the Brownian motion of water to show tissue microstructure. DTI based tractography has enabled probing of the tissue finer orientation from voxel to voxel in three dimensions. There has been a research trial using DTI to show the arrangement and measurement of the length of the columns and microstructures of the growth plate ¹⁶.

The purpose of the MR imaging of the knee is:

1. Evaluation of early degeneration of the knee joint including gross morphologic changes (conventional MR) as well as microstructure changes of the cartilage (quantitative MR).
2. Evaluation of growth plate abnormalities by measuring track length of the columnar cells of the growth plate (DTI).

The purpose of obtaining the MRI is not to assess the effects of GH on the joint disease. Our study will be underpowered to perform this assessment and as MRI evaluations are costly, we will only perform the MRI once at the baseline visit. This will be sufficient for the scientific purposes stated above.

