 - f. Frequency of joint complaints.

Study Recruitment

Only study participants that have had a satisfactory response to GH within the first year of treatment will have the opportunity to enroll in the extension trial. This is defined as an increase of height SDS of + 0.3 or greater.

Study protocol

This is an extension trial of rhGH therapy in pre-pubertal children with ACAN deficiency. The primary outcome measures of interest are height velocity and change in height SDS. All patients currently in the treatment trial will continue to receive once daily injections of Norditropin at a standard dose of 50 mcg/kg/day, per initial study protocol (this dose can only be adjusted based on safety guidelines as described in the original protocol for year 1 of therapy, i.e., if IGF-I concentration on therapy is $> +2.5$ SD)

Follow up visits will occur every 6 months, or semi-annually. Study staff will continue to perform check-in calls every 3 months to promote compliance and to record any missed doses, potential new adverse events or use of concomitant medications. In addition, study staff will dispense an additional 3 months of medication and supplies after the 3-month check confirms adequate adherence with the study protocol and no new treatment-related adverse events were reported. Each follow-up visit has a +/-2-week window to accommodate participant schedules and travel. These visits will be the same as previous ones performed for the initial 12-month trial.

The chart below outlines the visit activity schedule **for the extension trial**.

Lab/Assessment	Check-in Calls	18- and 30-Month Visits	24- and 36-Month Visits
Physical exam		X	X
Vital signs		X	X
Height/weight		X	X
TSH		X	X

Free T4		X	X
IGF-I		X	X
IGFBP-3		X	X
Bone Age X-ray			X
DXA scan (whole body, lumbar spine) *			X
Compliance Review	X		
Adverse Event Review	X		
Medication Dispensation	X	X	X

*Additional radiation will be received, approx. 0.013mSv per scan

Only if a participant was unable to complete a study procedure during the initial 12-month trial period due to age, scheduling conflicts, or illness, they may be asked to perform the procedure during the extension trial at one of their scheduled study visits (i.e., MRI, gait assessment, musculoskeletal evaluation).

After each study visit, we will send a letter summarizing the exam findings and lab results to the participant's local primary care physician or pediatric endocrinologist.

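### A missed baseline knee MRI may be made up after at least 12 months of GH, nothing separates such scans from untreated ones, and the quantitative MR values have no named reference

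*Combined protocol and SAP*

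**What the plan says.** **Aim.** Section 5, Joint Phenotyping Procedures, says of the knee MRI: "These imaging studies will provide insights into the pathological effects of mutations in ACAN on joint cartilage". The T2 and T1rho rationale is: "By measuring collagen fiber anisotropic changes (reflected by increased T2 values) in combination with GAG depletion". The second listed purpose is: "Evaluation of growth plate abnormalities by measuring track length of the columnar cells of the growth plate (DTI". The related secondary endpoint, B.g, is: "Frequency of cartilage disease based on MRI evaluation of the knee as described below".

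**Who is scanned.** "All first-degree relatives will be screened for the ACAN mutation identified in the primary subject in the family". Entry to phenotyping then depends on a positive result: "Any family member identified to carry the same mutation as the primary subject will be eligible for inclusion in the phenotyping protocol". MRI is limited to carriers under 20 who can manage it without sedation, generally from age 6. Non-carrier relatives are identified but not imaged.

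**When.** Section 5 states that MRI is done once, at baseline, and that measuring a GH effect on joints is not its purpose. Table 1 marks MRI in the screening column only. A later paragraph adds repeat scans every other year, but only for those with osteochondritis dissecans (OD) on initial imaging.

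**The exception.** Section 6, Study protocol, covers participants who could not complete a procedure in the initial 12 months because of age, scheduling or illness: "they may be asked to perform the procedure during the extension trial at one of their scheduled study visits". MRI is among the examples given.

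**Analysis.** Section 11 makes all outcomes descriptive. Section 5 says "We have elected not to have a control arm for two reasons", but those reasons concern the GH treatment question and recruitment to a randomised trial. They do not address a reference for the MRI.

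**The concern.** The MRI is there to describe the disease, so the useful scan is one in a carrier not yet exposed to study GH. Section 5 is written that way; Section 6 opens a second route. A scan taken by that route reflects the mutation and a year or more of GH together, and one image cannot divide the two. Growth-plate DTI is the most exposed measure: the trial's first hypothesis is that GH raises growth velocity, and the background section places bone elongation in the growth plate. These children are also a selected group, because only those with a satisfactory height response in year 1 may enter the extension.

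A second gap affects every quantitative scan. To call T2 or T1rho increased, or a column length abnormal, is to compare it with something. The study scans no unaffected person, and the documents name no normal range, cut-off or external series.

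At stake is how the imaging results can be worded: whether an ACAN summary silently includes treated knees, and whether a continuous MR value is presented as evidence of pathology without a comparator.

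**Working it through.** **1. The plan's own counts.** Section 5 assumes 10 treated subjects, each with one affected parent and one further affected relative.
- Carriers phenotyped: 10 × (1 + 1 + 1) = 30, as stated.
- Carriers under 20: 10 × (1 + 1) = 20, matching the stated figure of about 20.
- Unaffected people scanned: 0.

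The 20 counts carriers under the age limit, not scans. It includes any child too young for unsedated MRI.

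The only power figure in the documents is 90% for n = 10, and it concerns height SDS. With mean 0.407 and SD 0.343, the noncentrality is (0.407 / 0.343) × √10 = 3.75. A two-sided one-sample t-test at an assumed alpha of 0.05 then has 91.5% power, so the figure reproduces. It has no bearing on MRI, for which no power is claimed.

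**2. Timing, side by side.**
- Section 5 and Table 1: MRI once, at screening, before GH is shipped.
- Section 6: a missed MRI may be done at a scheduled extension visit. The chart lists months 18, 24, 30 and 36, each ± 2 weeks.
- No sentence in Sections 5, 6 or 11 says how a scan from the second route enters B.g or the T2, T1rho and DTI summaries.

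**3. Is the exception likely to be used for age?** Age at month m is entry age a + m/12. Take 6 as the guide age for unsedated MRI.
- A child with a ≥ 6 can be scanned at baseline.
- By month 36, the guide age is reached if a + 3 ≥ 6, that is a ≥ 3. Entrants aged about 3 to under 6 could therefore have a first scan on GH.
- A child entering at 2 is 5 at month 36 and may never be scanned.
- Section 5, Study type, mentions a four-year extension. On that reading the last visit is at 12 + 48 = 60 months, and a child entering at 2 would be 7.

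The documents give no entry ages, and age 6 is described as general practice, not a limit. This shows that such scans are foreseeable, not that they occurred.

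**4. Size.** If k of n first scans are on GH and GH shifts a measure by δ SD, the group mean moves by (k/n) × δ. None of k, n or δ is in the documents. On the planned count, n is at most about 20, so each on-GH scan has a weight of at least about 1/20 = 5%. With δ assumed at 0.5 to 1.0 SD, one scan out of 20 moves the mean by 0.025 to 0.05 SD. With k = 0 there is no effect.

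**5. The missing reference.** With about 20 carriers and no unaffected subjects, the study data cannot estimate an affected-versus-unaffected difference. Adding controls would help only with large differences. For 20 versus 20 (two-sided alpha 0.05, 80% power, independent observations), the detectable difference is (1.96 + 0.84) × √(1/20 + 1/20) = 0.89 SD by the normal approximation, or 0.91 SD by the t-test. For 10 versus 10 the t-test gives 1.33 SD. Family clustering would make these worse. Limiting the claim is therefore more practical than adding scans.

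**The case against.** The strongest reply is that the plan is already descriptive. Section 4 sets out to describe features, and Section 11 plans no formal comparison. The sentence on T2 and GAG explains what the sequences reflect; it does not classify anyone as diseased. The make-up clause is narrow and conditional, and relatives outside the treatment trial get no study GH. Morphologic findings can be read without controls, and the only MRI frequency reported, OD in 25% of pediatric patients, is of that kind.

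Most of this stands, and it keeps the point small. It does not remove it. Section 5 speaks of degeneration, growth-plate abnormalities and effects of the mutation, which go beyond bare description. A descriptive summary can still mix exposed and unexposed scans.

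Three stronger readings are tempting and are not supported:
- **Late scans will be pooled, or are already in the 25%.** The documents describe no pooling. They say the initial phenotype arm was complete in November 2019, but not whether any late first scan occurred. What can be said is that no rule separates them.
- **A given share of scans is affected.** The number is not stated, and the figure of about 20 counts carriers, not scans.
- **B.g cannot be answered, or must be redefined as morphology only.** The lack of a numeric cut-off is missing detail. Narrowing B.g now, with the OD result known, would be a result-informed change to an endpoint.

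**Conclusion.** The concern holds in limited form. Sections 5 and 6 disagree on when the first MRI may be taken. Followed as written, Section 6 admits scans after at least 12 months of GH as phenotyping scans, with nothing to keep them apart from untreated ones. Separately, the quantitative MR values have no reference, so they can be described but not called increased or abnormal, or attributed to ACAN deficiency.

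The timing issue affects an unknown number of treated children, possibly none. The reference issue affects every T2, T1rho and DTI value. No stated figure is wrong, and the height endpoints are unaffected. The conclusion assumes that a made-up MRI would serve as that child's phenotyping scan, which is the natural reading of the clause, and that the child is still on GH at the extension visit. This is a cheap improvement, not a flaw that threatens the trial.

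**What to change.** 1. Reconcile Section 5 and Table 1 with the make-up clause in Section 6, so that both state when a first MRI may be taken.
2. Classify every first MRI as pre-GH/untreated or on-GH. For treated children, use the scan date and the GH start date that Section 5 already requires to be recorded. For relatives outside the treatment trial, use the medical-history questionnaire to confirm that they had no GH elsewhere.
3. Base B.g and the T2, T1rho and DTI summaries on pre-GH scans of treated children plus scans of GH-untreated carriers. List on-GH first scans separately, with time on GH. Leave the definition of B.g otherwise as it is.
4. Add to the MRI paragraphs of Section 5 that T2, T1rho and DTI track length are reported descriptively against age. They will not be called increased or abnormal, or attributed to ACAN deficiency, unless compared with a named age-matched reference.

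**Cost.** Wording and one derived variable; no new scans, participants or readers. The denominator may be slightly smaller, and the quantitative sequences support a narrower claim. The documents do not say that a suitable reference exists, so item 4 may leave these measures purely descriptive.
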